3 STUDY VARIABLES

3.1 Group variables

Allocated protocol according to randomisation.

- M4 (Study group)
- NICE (Control group)

Each protocol categorises subjects in high-and low-risk of ectopic pregnancy:

- M4 use polynomial logistic regression to estimate the probability (%) of a PUL being a failed PUL, IUP and EP. M4 categorise a PUL as high-risk if the calculated probability of an EP $\geq 5\%$. If the calculated risk of an EP is $<5\%$ a PUL is categorised as low-risk and either a failed PUL or an IUP is predicted depending on which that has the highest calculated probability.

STATISTISKA KONSULTGRUPPEN		Statistical Analysis Plan
Protocol: Management of pregnancies of unknown location- a randomised controlled trial of two hCG-based decision support models.	Version: 1.0	Page 9 of 18

- For NICE: A PUL with a rise in hCG level of more than 63% or a decline of more than 50% it is categorised as low risk of being an EP, while a change in hCG levels between these cut-offs indicates high risk for EP.

3.2 Screening variables

Data collected for screened but not included subjects will include (not defined in study populations)

- Date of last screening made for a subject not included in the study (yy/mm/dd).
- Age at screening (years)
 - Reason for exclusion (Known pregnancy location (IUP)/Known pregnancy location (EP)/In-patients/Decline to participate in the study/Do not understand oral or written study information/Other reasons)
 - If IUP (with Yolk sac/Foetus with heartbeat/Foetus without heartbeat/Missed abortion/Complete miscarriage/ Incomplete miscarriage/Anembryonic pregnancy)
 - If EP (with Yolk sac/Foetus with heartbeat/Foetus without heartbeat)
 - EP location (fallopian tube/ovary/interstitium/caesarean scar/cervical)
 - EP size (mm)
- Screening site (SUS/SÄS/SkaS)

3.3 Baseline Variables

- Age (years)
- BMI (kg/m²)
- Smoking (Never smoked/Former smoker/current smoker<10/11-20/21-30/>30)
- Number of prior pregnancies with:
 - miscarriage ≤ 12 weeks
 - miscarriage >12 weeks < 22 weeks
 - legal abortion
 - vaginal delivery
 - caesarean section
 - ectopic pregnancy
- History of infertility (Yes/No)
- Pregnancy conceived with IVF (Yes/No)
- Treated for chlamydia infection (Yes/No)
- Cervical dysplasia (Yes/No)

STATISTISKA KONSULTGRUPPEN		Statistical Analysis Plan
Protocol: Management of pregnancies of unknown location- a randomised controlled trial of two hCG-based decision support models.	Version: 1.0	Page 10 of 18

- Intrauterine device (Yes/No)
- Undergone gynaecological surgery (Yes/No)
 - Ovarian cyst (Yes/No)
 - Pelvic infection (Yes/No)
 - Endometriosis (Yes/No)
 - Ectopic pregnancy (Yes/No)
 - Excision of surgical dysplasia (Yes/No)
 - Uterine fibroids (Yes/No)
 - Polyp (Yes/No)
- Pregnancy weeks according to last menstrual period or embryo transfer date
- Ethnicity (Caucasian/African/Asian/Other)

3.4 First visit data variables

- Presenting symptoms
 - Bleeding (Yes/No)
 - Pain (Yes/No)
 - Pregnancy dating (Yes/No)
 - Previous early pregnancy complication (Yes/No)
 - IUD concerns (Yes/No)
- Self-registered lower abdominal pain (scale 1-10)
- Duration of pain in days
- Primary site of pain (right/left/general)
- Bleeding characteristics
 - Brown discharge (Yes/No)
 - Spotting (Yes/No)
 - As a menstruation (Yes/No)
 - More than a menstruation (Yes/No)
 - With clots (Yes/No)
- Physician seniority (resident/specialist/senior consultant)
- Years of transvaginal ultrasound experience (<1/1-3/>3)
- Type of pregnancy of unknown location at the first transvaginal ultrasound (No sign of IUP or EP/Probable IUP/Probable EP).
 - If Probable IUP
 - intrauterine sac like structure (Yes/No)
 - Size (mm)
 - retained products of conception (Yes/No)

STATISTISKA KONSULTGRUPPEN		Statistical Analysis Plan
Protocol: Management of pregnancies of unknown location- a randomised controlled trial of two hCG-based decision support models.	Version: 1.0	Page 11 of 18

- Anembryonic pregnancy (Yes/No)
- If Probable EP
 - inhomogeneous adnexal mass, 'blob' sign (Yes/No)
 - Size (mm)
 - extrauterine sac-like structure, 'doughnut' sign (Yes/No)
 - If Yes (fallopian tube/ovary/interstitium/caesarean scar/cervical)
 - Size (mm)
- Endometrial thickness (mm)
- Fluid in the pouch of Douglas (Yes/No)
- Amount of fluid (mm)
- Echogenic masses suggesting haemoperitoneum (Yes/No)

3.5 HCG related variables

- hCG1-value (IU/L)
- hCG2-value (IU/L)
- Mean of hCG1 and hCG2 (IU/L)
- Ratio of hCG1/hCG2
- Time between the first and second hCG measure (hours)

3.6 Randomisation and follow-up variables

- Randomisation (Yes/No)
 - If No (Hospitalisation before the second hCG/First hCG > 10 000 IU/L/Time between the first and second hCG measurement are less than 44 hours or more than 56 hours/The subject decline further participation or did not show up for a second hCG measurement)
- Categorisation and predicted outcome of PUL by allocated group: M4 or NICE (High risk, EP/Low risk, failed PUL/Low risk, IUP).
- Recommended follow-up by allocated group (Urine pregnancy test after two weeks/Ultrasond examination after one week/TVU examination within 24-48 hours)
- Deviation from recommended follow-up due to:
 - Follow-up visit was scheduled to early or late by the nurse (Yes/No)
 - The physician departed from plan due to concerns regarding other clinical variables (Yes/No)
 - The physician departed from plan due to concerns regarding ultrasound finding (Yes/No)
 - The patient made an unplanned visit due to increased pain or bleeding (Yes/No)

STATISTISKA KONSULTGRUPPEN		Statistical Analysis Plan
Protocol: Management of pregnancies of unknown location- a randomised controlled trial of two hCG-based decision support models.	Version: 1.0	Page 12 of 18

3.7 Treatment

- First line treatment (surgical/medical/expectancy)
- Second line treatment (surgical/medical/expectancy)
- Third line treatment (surgical/medical/expectancy)
 - If surgical (laparoscopic salpingectomy/laparoscopic salpingotomy/no finding/uterine evacuation)
 - Histopathological examination (Yes/No)
 - Confirmed pregnancy tissue (Yes/No)
 - Blood loss (<100/100-300/>300-500/>500-1000/>1000-1500/>1500 ml)
 - Blood transfusion (yes/no)
 - If medical
 - Methotrexate (single dose/repeat dose)
 - Change in hCG levels between days four and seven after injection (%)
 - Misoprostol (single dose/repeat dose)
- Complication
 - Rupture of ectopic pregnancy (Yes/No)
 - Serious side effect of methotrexate (Yes/No)
 - If Yes (Hepatotoxicity/Nephrotoxicity/Pulmonary toxicity/Infection/Myelosuppression)
 - Infection after surgery (Yes/No)
 - If Yes (Tubo-ovarian abscess/Salpingitis/Wound infection)
 - Reoperation due to persistent trophoblast (Yes/No)
 - Reoperation due to bleeding Yes/No)
- Time from randomisation until diagnosis, known outcome of PUL or start of first line treatment (days)
- Time from randomisation until last clinical visit, discharge after surgery or contact by telephone (days)
- Time from diagnosis until resolution of hCG (level < 5.0 IU/L) in ectopic pregnancies and persistent PUL managed expectantly, treated with methotrexate (days) or conservative surgery (salpingotomy)

3.8 Transvaginal ultrasound (TVU) and hCG

- First visit TVU findings (Pregnancy of unknown location/probable IUP/probable EP/IUP/EP)
 - If Probable IUP
 - intrauterine sac like structure (Yes/No)
 - Size (mm)

STATISTISKA KONSULTGRUPPEN		Statistical Analysis Plan
Protocol: Management of pregnancies of unknown location- a randomised controlled trial of two hCG-based decision support models.	Version: 1.0	Page 13 of 18

- retained products of conception (Yes/No)
- If Probable EP
 - inhomogeneous adnexal mass, 'blob' sign (Yes/No)
 - Size (mm)
 - extrauterine sac-like structure, 'doughnut' sign (Yes/No)
 - If Yes (fallopian tube/ovary/interstitium/caesarean scar/cervical)
 - Size (mm)
- If IUP (Yolk sac/Foetus with heartbeat/ Foetus without heartbeat/ Missed abortion/Complete miscarriage/Incomplete miscarriage/ Anembryonic pregnancy)
 - Size (mm)
- If EP (with Yolk sac/Foetus with heartbeat/Foetus without heartbeat).
 - EP location (fallopian tube/ovary/interstitium/caesarean scar/cervical)
 - EP size (mm)
- Second visit TVU findings are described with the same variables as for the first visit TVU findings (Pregnancy of unknown location/probable IUP/probable EP/IUP/EP)
- Third visit TVU findings are described with the same variables as for the first visit TVU finding (Pregnancy of unknown location/probable IUP/probable EP/IUP/EP)
- Fourth visit TVU findings are described with the same variables as for the first visit TVU finding (Pregnancy of unknown location/probable IUP/probable EP/IUP/EP)
- Fifth visit TVU findings are described with the same variables as for the first visit TVU finding (Pregnancy of unknown location/probable IUP/probable EP/IUP/EP)
- Sixth visit TVU are described with the same variables as for the first visit TVU finding (Pregnancy of unknown location/probable IUP/probable EP/IUP/EP)
- Seventh visit TVU are described with the same variables as for the first visit TVU finding (Pregnancy of unknown location/probable IUP/probable EP/IUP/EP)
- Eight visit TVU findings are described with the same variables as for the first visit TVU finding (Pregnancy of unknown location/probable IUP/probable EP/IUP/EP)
- First visit hCG level (IU/L)
- Second visit hCG level (IU/L)
- Third visit hCG level (IU/L)
- Fourth visit hCG level (IU/L)
- Fifth visit hCG level (IU/L)
- Sixth visit hCG level (IU/L)
- Seventh visit hCG level (IU/L)
- Eight visit hCG level (IU/L)
- Ninth visit hCG level (IU/L)

STATISTISKA KONSULTGRUPPEN		Statistical Analysis Plan
Protocol: Management of pregnancies of unknown location- a randomised controlled trial of two hCG-based decision support models.	Version: 1.0	Page 14 of 18

- Tenth visit hCG level (IU/L)
- Eleventh hCG level (IU/L)
- Twelfth visit hCG level (IU/L)
- Number of days between measurement of hCG two and three (needs to be calculated)
- Number of days between measurement of hCG two and three (needs to be calculated)
- Number of days between measurement of hCG three and four (needs to be calculated)
- Number of days between measurement of hCG four and five (needs to be calculated)
- Number of days between measurement of hCG five and six (needs to be calculated)
- Number of days between measurement of hCG six and seven (needs to be calculated)
- Number of days between measurement of hCG eight and nine (needs to be calculated)
- Number of days between measurement of hCG nine and ten (needs to be calculated)
- Number of days between measurement of hCG ten and eleven (needs to be calculated)
- Number of days between measurement of hCG eleven and twelve (needs to be calculated)
- Number of days between measurement of hCG twelve and thirteen (needs to be calculated)
- Number of days between measurement of hCG thirteen and fourteen (needs to be calculated)

3.9 Efficacy Variables

3.9.1 Primary Efficacy Variables

- Ectopic pregnancy (EP) (Yes/No)
 - If yes (Tubal Ampulla/Tubal Isthmus/Interstitium/Ovary/Caesarean scar/cervical)
- Intrauterine pregnancy (IUP) (Yes/No)
 - If yes (Viable IUP/Non-viable IUP /Non-viable IUP (Missed abortion/Anembryonic pregnancy)/Complete miscarriage/Incomplete miscarriage/cervical)
- Failed PUL (Yes/No)
- Persistent PUL, will be incorporated among EP in the analyses (Yes/No)
 - If yes (Treated/Resolved (untreated))
- Risk of ectopic pregnancy (High/Low)

STATISTISKA KONSULTGRUPPEN		Statistical Analysis Plan	
Protocol: Management of pregnancies of unknown location- a randomised controlled trial of two hCG-based decision support models.		Version: 1.0	Page 15 of 18

3.9.2 Secondary Efficacy and Safety Variables (clinical outcomes)

- Number of TVU performed
- Number of hCG measurements
- Number of surgical procedures
- Time from randomisation until diagnosis, known final outcome of PUL or start of first line treatment (days)
- Time from randomisation until last clinical visit, hospital stay or contact by telephone (days)
- Time from diagnosis until resolution of hCG in EP and persistent PUL managed expectantly or treated with methotrexate (days) (calculated from the previous two variables by subtracting the second from the first)

Adverse events

- Accidental disruption of a possibly viable IUP (Yes/No)
- Ruptured EP (Yes/No)
- Emergency surgery (Yes/No)
- Adverse effect of Methotrexate (Yes/No)
- Negative laparoscopy (Yes/No)
- Unplanned visits initiated by the patient (Yes/No)
- Perioperative blood loss (ml)
- Blood transfusion (Yes/no)

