4.9.2 Secondary Efficacy Analyses

Summary of all secondary variables will also be presented totally and by randomised groups and by risk category (seven columns) as described in general methods above. This will be made for both FAS and per-protocol population.

STATISTISKA KONSULTGRUPPEN		Statistical Analysis Plan	
Protocol: Management of pregnancies of unknown location- a randomised controlled trial of two hCG-based decision support models.			
Version: 1.0		Page 17 of 18	

The main secondary analyses/questions will be evaluated:

1. Comparing the safety and effectiveness based on clinical outcomes between the allocated randomised groups.
2. Comparing the benefit of an ectopic pregnancy or a non-ectopic pregnancy being correctly categorised by a protocol versus those incorrectly categorised based on clinical outcomes.

A t-test will be used for comparison of continuous variables between independent groups. For comparison of proportions between groups a Fisher exact test is used. For comparison of number variables between groups a Mantel-Haenszel chi-square test is used.

Kaplan-Meier curves are used to report the time from randomisation to the diagnosis and/or start of treatment of an ectopic pregnancy and the last visit in the clinic which includes any visit related to PUL management and for all outcomes of PUL. This will be reported according to allocated randomisation group and for the total cohort.

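### SAP 3.9.2 derives time from diagnosis to hCG resolution from the date of last contact, not from hCG < 5.0 IU/L as in 3.7, and the subtraction is reversed

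*SAP*

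**What the plan says.** Section 3.9.2 of the SAP lists three time variables in sequence:

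- the first is "Time from randomisation until diagnosis, known final outcome of PUL or start of first line treatment (days";
- the second is "Time from randomisation until last clinical visit, hospital stay or contact by telephone (days";
- the third is the time from diagnosis to hCG resolution, for ectopic pregnancies and persistent PUL managed expectantly or with methotrexate. It is "calculated from the previous two variables by subtracting the second from the first".

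Section 3.7 lists the third variable as well, but with an explicit event and no subtraction rule: "Time from diagnosis until resolution of hCG (level < 5.0 IU/L) in ectopic pregnancies and persistent PUL managed expectantly". It goes on to include women treated with methotrexate or by salpingotomy; 3.9.2 does not mention salpingotomy.

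The last contact is described in two further places. Section 3.7 has "Time from randomisation until last clinical visit, discharge after surgery or contact by telephone (days", and section 4.9.2 has "the last visit in the clinic which includes any visit related to PUL management and for all outcomes of PUL". None of the three descriptions mentions an hCG value.

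For the analysis, 4.9.2 states: "A t-test will be used for comparison of continuous variables between independent groups".

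**The concern.** There are two faults in one parenthesis. The subtraction runs the wrong way, so it yields a negative number of days. More importantly, neither input carries the date on which hCG fell below 5.0 IU/L, so no combination of the two can give the quantity that the variable is named for and that 3.7 defines.

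If contact continues after resolution, the time is overstated. If contact ends before resolution, the time is understated and a woman who has not resolved is counted as though she had. As a continuous variable in days, the outcome falls under the t-test in 4.9.2, which has no way to represent an unresolved woman. The SAP would then report, under the name of hCG resolution, a result that partly reflects how long the clinic stayed in touch.

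**Working it through.** The plan gives no figure to reproduce, so the check is algebraic, followed by an illustration.

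**Definitions** (days from randomisation):

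- D = the date that ends the first variable in 3.9.2, taken here as diagnosis (3.9.2 also allows known outcome or start of first-line treatment);
- L = last contact, which ends the second variable in 3.9.2;
- R = first hCG below 5.0 IU/L, the event in 3.7.

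**Step 1, the rule as written.** Second subtracted from first is D − L. This is zero or negative whenever L is on or after D.

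**Step 2, the order reversed.** L − D is the time from diagnosis to last contact.

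**Step 3, the definition in 3.7.** This is R − D. Since L − D = (R − D) + (L − R), the error for one woman after the sign is corrected is the gap L − R. It is zero only when last contact falls on the day of resolution.

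**Step 4, illustration.** All day counts are assumed: D = 5 and R = 33, so the 3.7 definition gives 33 − 5 = 28 days.

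| Last contact L | As written, 5 − L | Reversed, L − 5 | Error after reversal, L − 33 |
|---|---|---|---|
| 26 | −21 | 21 | −7 |
| 33 | −28 | 28 | 0 |
| 40 | −35 | 35 | +7 |
| 47 | −42 | 42 | +14 |

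In the first row the woman has not resolved by her last contact, yet she is counted as resolved at 21 days.

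**Step 5, effect on a comparison.** Averaging step 3 within each group, the error in the group difference equals the mean gap in one group minus the mean gap in the other. If both mean gaps are 7 days, the error is 7 − 7 = 0. If they are 7 and 0, it is 7 − 0 = 7 days. The reversed sign alone changes the direction of a difference but not its size.

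**Step 6, does the SAP make L equal R?** No. Section 3.9.2 lets L be a hospital stay or a telephone call. Section 3.7 lets it be discharge after surgery, and also provides for surgery as second- or third-line treatment. Section 4.9.2 counts any PUL-related visit. Entry to the full analysis set (2.1.1) requires a known pregnancy outcome, which is not the same as resolved hCG.

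**Step 7, can R be obtained?** Yes, from the serial hCG values in 3.8 and their sampling dates. The listed intervals are not enough. Two-to-three appears twice, and after "Number of days between measurement of hCG six and seven (needs to be calculated" the list goes straight to eight-to-nine. With seven-to-eight missing, the intervals cannot be summed past the seventh measurement.

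**The case against.** The strongest reply is that this is loose wording. A time in days has an obvious direction, and any programmer would notice negative values. Within the subgroup named in 3.9.2, follow-up may well end when hCG resolves, and the protocol, which is not shown, may say so; last contact would then be a sound proxy. Section 3.9.1 codes persistent PUL as either treated or resolved untreated, which leaves no unresolved category among the untreated. The day counts are hypothetical, and nothing in the SAP shows that the gap between resolution and last contact would differ between the M4 and NICE groups. Finally, the first sample below 5.0 IU/L is itself an approximation, because resolution lies somewhere between two samples.

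Much of this stands. The sign is a slip with little consequence. The bias is conditional, and a zero error in the group comparison is possible. The sampling-interval point is also fair, although the first qualifying sample is at least tied to the event that 3.7 names.

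What does not stand is the assumption that last contact is the resolution visit. The SAP states this nowhere, and its descriptions of last contact allow ends that have nothing to do with hCG. The coding of untreated persistent PUL says nothing about ectopic pregnancies or treated cases. Section 4.9.2 also compares correctly with incorrectly categorised women. That comparison is not randomised, so equal gaps cannot be taken for granted there.

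**Conclusion.** The rule in 3.9.2 is wrong as written. It gives a non-positive duration, and with the order reversed it measures time to last contact rather than time to hCG below 5.0 IU/L. Both points follow from the text alone.

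The numerical effect cannot be determined from the document. It is zero for a woman whose last contact falls on the day of resolution, and otherwise equals the gap between the two dates. In a group comparison it equals the difference in mean gaps. The illustrated errors of −7 to +14 days rest wholly on assumed dates.

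The scope is narrow: one secondary variable, in ectopic pregnancies and persistent PUL managed expectantly or with methotrexate. The primary sensitivity and specificity are unaffected. It should be corrected because a named outcome has two conflicting definitions in the same plan.

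**What to change.** - Delete the parenthesis in 3.9.2 and define the variable as in 3.7: date of the first hCG below 5.0 IU/L minus date of diagnosis.
- Take the end date from the hCG sampling dates, not from the interval list in 3.8, and correct that list's duplicate and its gap.
- Censor women with no value below 5.0 IU/L at their last hCG measurement, and report the outcome by Kaplan-Meier, which 4.9.2 already uses for the times to diagnosis or treatment and to last visit.
- State whether women treated by salpingotomy are included, so that 3.7 and 3.9.2 agree.

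The cost is about one sentence in 3.9.2 plus code for the derived variable. The sampling dates must be brought into the analysis data; 3.8 already calls for intervals between hCG measurements to be calculated.

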4 STATISTICAL METHODOLOGY

4.1 General Methodology

Descriptive statistics will be presented by mean, standard deviation (SD), median, Q1 and Q3 (continuous variables) and number and percentage (categorical variables).

All tests will be two-tailed and conducted at the 0.05 significance level. All analyses will be performed by using SAS® v9.4 (Cary, NC).

4.2 Patient Disposition and Data Sets Analysed

The number of subjects screened, included in FAS and per-protocol population. Number of subjects lost to follow-up and reasons for exclusion from per-protocol population. Summary will be totally and by randomised groups and by risk category (seven columns).

4.3 Screening

Summary will be made totally and only for subjects who were not randomised.

4.4 Baseline

Summary will be totally and by randomised groups and by risk category (seven columns as described in general methods above. This will be made for both FAS and per-protocol population.

STATISTISKA KONSULTGRUPPEN		Statistical Analysis Plan
Protocol: Management of pregnancies of unknown location- a randomised controlled trial of two hCG-based decision support models.	Version: 1.0	Page 16 of 18

4.5 First visit data.

Summary will be totally and by randomised groups and by risk category (seven columns as described in general methods above. This will be made for both FAS and per-protocol population.

4.6 HCG relates.

Summary will be totally and by randomised groups and by risk category (seven columns as described in general methods above. This will be made for both FAS and per-protocol population.

4.7 Randomisation and follow-up

Summary will be totally and by randomised groups and by risk category (seven columns as described in general methods above. This will be made for both FAS and per-protocol population.

4.8 Treatment

Data will be presented for first-, second- and third-line treatments. Summary will be totally and by randomised groups and by risk category (seven columns as described in general methods above. This will be made for both FAS and per-protocol population.

4.9 Efficacy Analyses

4.9.1 Primary Efficacy Analysis

Diagnostic performance will be described with sensitivity, specificity, positive predictive value (PPV) and negative predictive value (NPV), positive and negative likelihood ratio (LR+, LR-). The sensitivity represents ectopic pregnancies (EP) and persistent PUL correctly categorised as high risk of being an EP and the specificity represents non-ectopic pregnancies (IUP and failed PUL) correctly categorised as low risk of being an EP. PPV represents EP among PUL categorised as high risk and NPV represents IUP and failed PUL among PUL categorised as low risk.

The primary analysis will be performed for both M4 and NICE protocols on cross-sectional data for all subjects in the FAS population. To test differences in sensitivity and specificity between M4 and NICE the sign test will be used.

In addition to the cross-sectional analysis above a sensitivity analysis will be conducted to test differences in diagnostic performance measures by randomised groups for the FAS population. An exact 95 % CI will be calculated for the difference in sensitivity between the groups. The same will be produced for the specificity.

Complementary analyses will also be conducted for the per-protocol population.

Summary of all primary variables will also be presented totally and by randomised groups and by risk category (seven columns) as described in general methods above. This will be made for both FAS and per-protocol population.

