1.2 Study Design

This study is a multicentre randomised comparative diagnostic and clinical impact trial of two hCG-based protocols for PUL management. The study has a superiority design regarding the primary outcome of specificity for non-ectopic pregnancies for M4, given that the primary outcome of sensitivity for ectopic pregnancies is not inferior (non-inferiority design) in comparison with hCG cut-offs recommended by NICE. The diagnostic performance of the protocols will be evaluated on all subjects as a cross-sectional study for the primary analysis as well by randomisation groups in a sensitivity analysis.

[figure not shown]

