1.4 Sample Size

1.4.1 Original sample size calculation

The sample size calculation was based on data from our previous study where M4 and the hCG cut-offs by NICE had a sensitivity of 89% and 86% for ectopic pregnancy respectively ($p=0.42$) (3). The specificity for non-ectopic pregnancy (IUP and failed PUL) was 78% and 70% respectively for M4 and the hCG cut-offs ($p=0.01$) (3).

The primary objective to test the superiority of M4 compared with NICE in specificity for non-ectopic pregnancies with 80% power. A reference specificity of 70% (NICE) is used. Considering eight percentage points to be a clinically important difference in specificity, given $\beta=20\%$, $\alpha=5\%$ and a two-sided test, 495 patients are needed per group to demonstrate superiority.

STATISTISKA KONSULTGRUPPEN		Statistical Analysis Plan
Protocol: Management of pregnancies of unknown location- a randomised controlled trial of two hCG-based decision support models.	Version: 1.0	Page 8 of 18

The primary objective will also test the non-inferiority of M4 to NICE in sensitivity for ectopic pregnancy. A reference sensitivity of 86% (NICE) is used and we would allow a one percentage point lower sensitivity for M4 and that the lower limit of the two-sided 95% CI for the difference between the two protocols should not exceed seven percentage points with a probability of 80% ($\beta=20\%$), to be a non-inferior difference. Given a significance level (α) of 5% and a two-sided test, 541 patients per randomisation group are needed.

In our previous study five percent of patients were lost to follow-up, while another study reported a 7% loss to follow-up [46]. We have estimated the maximum rate of loss to follow-up to be 10%. For protection against that 10% of patients will be lost to follow-up, a total of approximately 1200 patients are needed.

1.4.2 *Cross-sectional sample size calculation*

No sample size calculation was performed a priori. A post-hoc power analysis will be performed.

1.4.3 *Secondary outcomes*

No sample size calculation was performed for secondary outcomes.

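### The paired primary analysis tests sensitivity only for no difference, so it does not assess the non-inferiority on which M4's specificity claim depends

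*SAP*

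**What the plan says.** Section 1.2 describes a conditional claim. M4 is to be shown superior in specificity, "given that the primary outcome of sensitivity for ectopic pregnancies is not inferior (non-inferiority design").

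Section 1.4.1 gives the criterion. "A reference sensitivity of 86% (NICE) is used", "we would allow a one percentage point lower sensitivity for M4", and "the lower limit of the two-sided 95% CI for the difference between the two protocols should not exceed seven percentage points".

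Section 4.9.1 sets out the analysis itself. "The primary analysis will be performed for both M4 and NICE protocols on cross-sectional data for all subjects in the FAS population", so every subject is classified by both protocols and the comparison is paired. The only inferential method named for it is: "To test differences in sensitivity and specificity between M4 and NICE the sign test will be used". Section 4.1 adds: "All tests will be two-tailed and conducted at the 0.05 significance level".

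The next paragraph of 4.9.1 introduces a sensitivity analysis by randomised group and continues: "An exact 95 % CI will be calculated for the difference in sensitivity between the groups". Section 6 confirms that the randomised comparison of diagnostic performance is now a sensitivity analysis only.

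**The concern.** The hypothesis and the test do not match. Non-inferiority requires rejecting the hypothesis that M4's sensitivity is at least 7 points lower than NICE's. A two-sided sign test addresses a different null, that the two sensitivities are equal. A non-significant result may reflect only a small number of EPs, and a significant result against M4 may reflect a difference well inside the margin.

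The mismatch appears to have arisen when the primary analysis moved from randomised groups to paired data. Section 6 explains that move but does not carry the margin, the interval or the order of testing across. Section 4 contains no margin, no paired interval, and no rule linking the sensitivity result to the specificity claim.

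The condition protects against EPs being put in the low-risk category. As written, the primary analysis yields no statistic that decides that half of the objective. If the sponsor fell back on non-significance as the pass criterion, the gate would become easier to pass as EPs became fewer.

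**Working it through.** **1. The plan's own figure.** Inputs from section 1.4.1: sensitivity 86% (NICE) and 85% (M4), margin 7 points, two-sided 95% CI (one-sided 0.025), power 80%.

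n per group = (1.960 + 0.842)² × (0.86×0.14 + 0.85×0.15) / (0.07 − 0.01)² = 7.849 × 0.2479 / 0.0036 = 540.5, rounded up to 541.

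This matches the stated 541 exactly. The design was therefore built on a 7-point margin that the primary test does not use.

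**2. Assumptions for the paired analysis.** The SAP gives neither the number of EPs nor the discordance rate (the share of EPs that the two protocols classify differently). One reference count is 108: 1200 × 0.9 = 1080 evaluable subjects, with an assumed 10% EP. Persistent PUL counts as EP in the SAP and would raise this, so a range of counts is shown. Discordance is taken as 10%, 15% and 20%.

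**3. Sign test when M4 is exactly at the margin.** With n EPs, discordance ψ and true difference −0.07, the number of discordant pairs is m ~ Bin(n, ψ). Each discordant pair favours M4 with probability (ψ − 0.07)/(2ψ), which is 0.15, 0.267 and 0.325 for the three values of ψ. Summing over all outcomes with exact two-sided p > 0.05 gives the probability of a non-significant result:

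| EPs | ψ = 10% | ψ = 15% | ψ = 20% |
|---|---|---|---|
| 100 | 0.49 | 0.65 | 0.73 |
| 108 | 0.44 | 0.62 | 0.71 |
| 200 | 0.12 | 0.32 | 0.45 |
| 216 | 0.09 | 0.28 | 0.41 |
| 300 | 0.02 | 0.13 | 0.25 |

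Under the same truth, the rule that the lower limit of a paired 95% score (Tango) interval lies above −7 points passes in about 2% to 3% of trials at every size tried.

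**4. Worked examples** (M4-only correct vs NICE-only correct, exact sign test, Tango interval for M4 minus NICE):

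- 3 vs 10 among 108 EPs: p = 0.09; difference (3 − 10)/108 = −6.5 points; 95% CI −13.9 to +0.1. Not significant, yet non-inferiority is not shown.
- 0 vs 6 among 216 EPs (a larger count than in the first example): p = 0.03 against M4; difference −2.8 points; 95% CI −5.9 to −1.0. Significant against M4, yet inside the margin.
- 5 vs 17 among 500 EPs: p = 0.017 against M4; difference −2.4 points; 95% CI −4.5 to −0.6. The same conflict.

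**5. Power of the correct rule.** If M4 is truly 1 point worse, simulation (10,000 runs per setting, discordance 10% to 20%) gives non-inferiority power of 25–38% with 100 EPs, 46–70% with 200, 64–88% with 300 and 87–99% with 541.

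**The case against.** Several points on the other side have force.

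- A sign test significantly in favour of M4 would show superior sensitivity, and hence non-inferiority. The earlier data in section 1.4.1 (89% vs 86%) lean that way. This stands, so it would be too strong to say that the test can never support the claim. It cannot do so when M4 is equal or slightly worse, which is the case the plan was sized for.
- The SAP nowhere says that a non-significant sign test will be read as non-inferiority. This also stands. The table in step 3 describes what would follow under that reading, not a rule the SAP states.
- The size depends heavily on the EP count. At 300 EPs with 10% discordance the false-pass probability is already close to nominal.
- The reverse error, significant against M4 yet non-inferior, needs a larger EP count. At 108 EPs even 0 vs 6 has a lower limit of −11.6 points. It becomes possible only from about 183 EPs.
- It might be argued that the margin in 1.4.1 and the exact interval in 4.9.1 together supply the rule. They do not. That interval is between groups, section 3.1 defines group as randomised allocation, and nothing ties the interval to the margin.
- The protocol is not shown, but it is unlikely to hold the missing rule, since section 6 presents the cross-sectional primary analysis as a departure from it.

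These points limit how the size should be stated. None of them supplies a decision rule for the paired analysis.

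**Conclusion.** The concern holds. Sections 1.2 and 1.4.1 state a non-inferiority condition with a 7-point margin. Section 4.9.1 replaces it, for the primary analysis, with a test of equality that does not address it.

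The textual gap rests on no assumption. Its numerical size is conditional on non-significance being taken as a pass, and on assumed EP counts and discordance. Under those conditions the chance of passing an M4 that is 7 points worse is 0.44 to 0.71 at 108 EPs, falling to 0.02 to 0.25 at 300, where a valid test allows 0.025. The sign test remains suitable for the paired specificity comparison.

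**What to change.** In section 4.9.1, replace the single sentence on the sign test with an ordered rule:

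1. **Sensitivity.** Among EP plus persistent PUL, report the paired difference M4 minus NICE with a two-sided 95% CI by a named paired method (for example the Tango score interval). M4 is non-inferior if the lower limit is above −7 percentage points, the margin already in 1.4.1.
2. **Specificity.** Only if step 1 is met, test specificity with the sign (exact McNemar) test at two-sided 0.05, and give a paired 95% CI for the difference.

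State that the sign test is not the decision rule for sensitivity, and record in section 6 how the non-inferiority criterion carries over to the paired analysis.

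The cost is SAP wording and a few lines of code, with no new data. Two consequences should be faced openly. With around 100 EPs the correct gate would usually fail even if M4 were only 1 point worse (power 25–38%), so the expected number of EPs should be stated alongside it. Section 6 says the move to paired data preceded database lock, but not whether the database is still open. If it has since been locked, the amendment should be dated and its timing relative to any analysis disclosed.
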